### **10.2 Secondary Endpoints**

There are no secondary endpoints.

### **10.3 Other Objectives/Measurements**

The additional objectives are described below along with planned statistical methods and analysis data to be used.

- Characterize HF sensors for the association with risk for VT/VF therapy
  - This will be assessed using an odds ratio
  - All subjects with usable sensor and episode data will be included in the analysis
- Characterize HF sensors for phenomapping of HF events
  - This will be assessed using cluster analysis
  - All subjects with a HF event and usable sensor data will be included in the analysis
- Characterize HF sensors for association with non-HF hospitalizations (including cardiac non-HF events and non-cardiac events)
  - This will be assessed using a paired t-test
  - All subjects with a non-HF hospitalizations and usable sensor data will be included in the analysis
- Collect Sleep Incline Sensor data leading up to clinical events: Subjects who were enrolled in a remote monitoring program using sleep incline data will be excluded and sensor data in the remaining patients will be analyzed using a paired t-test.
- Link study data to third-party data sources. Data linkage will be included in the analysis to assess feasibility to link to claims data (see Section 9.5) and other data sources. The linked data set will be used to compare claims-based events with study RCEs, assess the accuracy of claims-based algorithms to identify sensor detected events, and estimate the cost savings from avoidable hospitalizations. Comparisons will be made using paired and un-paired t-tests and receiver operator curve (ROC) analyses.

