
Inclusion Criteria
	
 
• Subject is age 18 or above, or of legal age to give informed consent specific to each country and national laws.
 
• Subject has a documented diagnosis of heart failure.
 
• Subject has a Boston Scientific CRT-D or ICD device implant that has HeartLogic, with Heart Failure Sensors turned ON, Respiratory Sensor turned ON, and Sleep Incline Sensor turned ON.
 
• Subject has an active bipolar RV lead implant.
 
• Subject is enrolled in LATITUDE (NXT 5.0 or future version), and is willing to be remotely monitored from the baseline visit for approximately 12 months with HeartLogic disabled.
 

Exclusion Criteria
	
 
• Subject has received or is scheduled to receive a heart transplant or ventricular assist device (VAD).
 
• Subject is enrolled in any concurrent clinical study without prior Boston Scientific written approval (excluding registries).
 
• Subject has a life expectancy of less than 12 months.
 
• Subject has a history of non-compliance to medical care or known inability to comply with requirements of the clinical study protocol.
 

Statistical Methods	
Primary Statistical Hypothesis	There is no statistical hypothesis. The primary objective of the PREEMPT-HF study is to investigate association between HF sensor data and 30-day HF readmissions.
Statistical Test Method	
The following statistical analyses will be used to evaluate the objectives of the study:
 
Primary Objective                      The difference in sensor trends pre-admission and post-discharge will be compared between subjects with and without a 30-day HF readmission. The comparison will be evaluated using a two-sample t-test for each HF sensor measurement.
 
Additional Objectives
 
 
1. Association with risk for device VT/VF: will be evaluated using an odds ratio.
 
2. Phenomapping of HF events: will be evaluated using cluster analysis.
 
3. Association with non-HF hospitalizations including cardiac non-HF events and non-cardiac events: will be evaluated using a paired t-test for each HF Sensor.
 

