- (2) *Characterize HF sensor data for association with risk of tachyarrhythmias and device therapy*: Acute HF exacerbations are presumed to trigger atrial and ventricular tachyarrhythmias through a number of mechanisms including increased cardiac filling pressure and neurohormonal activation; however patient risk assessment for malignant arrhythmias is subjective and device sensor based algorithms for risk stratification using traditional device sensors have had only modest accuracy. Similarly, a new onset or worsening of atrial or ventricular tachyarrhythmia may itself be a trigger for worsening of HF. The PREEMPT-HF study will investigate the association between the HeartLogic Index and patient risk for device ventricular tachycardia/fibrillation (VT/VF) therapy.

- (3) *Characterize HF sensor data for phenomapping of HF events*: Clinical practitioners have recognized that HF is comprised of multiple heterogeneous entities including HF with reduced, preserved, and mid-range ejection fraction (HFrEF, HFpEF, and HFmEF). Similarly, acute worsening HF has been classified by hemodynamic profiles incorporating congestion (wet/dry) and perfusion (warm/cold). However, physiological measurements underlying clinical classifications exhibit significant variation. For example, even though the majority (>80%) of patients admitted for worsening HF show clinical signs or symptoms of volume overload, there is a wide distribution of body fluid and its composition. Data driven approaches such as cluster analysis has been applied to phenotype HFrEF and HFpEF, but continuous data collected by implanted devices have not been utilized. The PREEMPT-HF study will collect data to investigate machine learning and clustering approaches for event classification using HF sensor data and baseline clinical variables. This type of unbiased dense phenotype mapping is known as phenomapping.

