#### 10.1.2 Sample Size

Approximately 3750 enrollments will be required for this study. The sample size was determined based on the estimated number of HF index hospitalizations and 30-day HF readmissions needed to evaluate the primary objective. Final sample size will be determined by an interim analysis as described in Section 10.9. An index HF hospitalization refers to the first HF hospitalization during the study follow-up period. A HF hospitalization is deemed usable if sensor data is available during the event and sufficient follow up time is recorded to determine if a readmission occurs.

A total of 215 usable index HF hospitalizations are required to have at least 80% power to detect a standardized difference of 0.5 in the mean sensor change (admission – discharge) between the groups with and without a 30-day HF readmission. It is expected that of the 215 index HF hospitalizations, 43 will be followed by a 30-day readmission (20%).

A total of 215 usable index HF hospitalizations was determined based on the following assumptions:

- 80% Power to detect a standardized mean difference of 0.5 between groups
- Two-sided type I error (alpha) of 0.05
- 3:1 ratio of group sizes (no-readmission : 30-day HF readmission), where the no-readmission group will exclude index HF hospitalizations with 31 to 60-day readmissions

Assuming a 20% loss of usable HF events due to proximity to study start and exit (completion or withdrawal), a total of 270 index HF hospitalizations are required to obtain 215 usable HF hospitalizations.

Approximately 3750 enrollments are required to obtain the 270 required index HF hospitalizations. This was determined based on the following assumptions:

- 9 % index HF hospitalization rate per patient year
- 20% death/withdrawal rate throughout duration of study
- Average of 12 months of sensor data per subject

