##### **10.5.2 Additional analyses**

- All subjects with usable sensor and episode data will be included in the analysis of characterizing HF sensors for the association with risk for device VT/VF therapy
- All subjects with a HF event and usable sensor data will be included in the analysis of characterizing HF sensors for phenomapping of HF events
- All subjects with a non-HF hospitalization and usable sensor data will be included in the analysis of characterizing HF sensors for association with non-HF hospitalizations

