**Table 24-2: Definitions**

Term	Definition
HeartLogic	HeartLogic is a diagnostic tool that includes a composite index monitored over time designed to deliver proactive alerts of worsening heart failure to clinicians.
LATITUDE	Consists of a patient communicator for transmitting device data, weight scale and blood pressure monitor, and a website for clinicians to review data
MEDDEV	European directive on medical devices
RAVE	The electronic data base used for the clinical trial
Source data	All information in original records and certified copies of original records of clinical findings, observations, or other activities in a clinical trial necessary for the reconstruction and evaluation of the trial. Source data are contained in the source documents (original records or certified copies).
Source documents	Original documents, data, and records

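### Does naming an odds ratio for the VT/VF therapy objective commit the study to an untimed per-subject table that unequal follow-up would bias?

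*Protocol*

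**What the plan says.** Section 10.3 introduces its list with "The additional objectives are described below along with planned statistical methods and analysis data to be used". For VT/VF therapy the entry is "This will be assessed using an odds ratio". The synopsis agrees: "Association with risk for device VT/VF: will be evaluated using an odds ratio". Section 10.5.2 gives the set: "All subjects with usable sensor and episode data will be included in the analysis of characterizing HF sensors", here for risk of device VT/VF therapy. None of the three places names the unit of analysis (subject, day or episode), a cut-off for a raised sensor value, or a window linking sensor state to therapy.

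The rationale in section 3.1 says that the study will "investigate the association between the HeartLogic Index and patient risk for device ventricular tachycardia/fibrillation (VT/VF) therapy". Table 24-2 describes HeartLogic as including "a composite index monitored over time designed to deliver proactive alerts of worsening heart failure to clinicians". Section 10.1.2 assumes a "20% death/withdrawal rate throughout duration of study". Section 8.2 lets data up to withdrawal be used, and Table 6-1 puts the final visit at 350 to 430 days from baseline, or at withdrawal. Sections 10.1 and 10.6 call the study exploratory, without formal tests or multiplicity adjustment. Sections 10.10 to 10.13 rely on a separate statistical analysis plan for subgroups, pooling, multivariable analyses and changes to planned analyses.

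**The concern.** The exposure changes from day to day, the outcome is an event in time, and follow-up differs between subjects. An odds ratio from one record per subject ignores all three. A subject who leaves at three months has had less opportunity both to show a raised state and to receive therapy than one followed for a year. Pooling such subjects in one table creates a positive association where there is none.

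Direction is a second worry. Section 3.1 itself says that "a new onset or worsening of atrial or ventricular tachyarrhythmia may itself be a trigger for worsening of HF", so an untimed table could count raised states that came after the therapy. If the analysis were done that way, early exits or reverse causation could be mistaken for a sensor signal that marks arrhythmic risk.

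**Working it through.** The protocol gives no figure for this objective, so there is none to reproduce. The check has three parts.

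**1. How large is the artefact in the feared analysis?**

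Inputs from the protocol: 20% death/withdrawal and about 3750 enrolments (section 10.1.2; the two are linked by 270/(0.09 × 0.80) = 3750), and final visit at 350-430 days (Table 6-1). Assumed, because the protocol gives no values: first raised states at rate *a* = 0.5-2 per year, therapies at rate *b* = 0.05-0.10 per year, the two independent, with early exits uniform over 0-365 days and the rest uniform over 350-430 days. Mean follow-up is then 0.20 × 182.5 + 0.80 × 390 = 348.5 days, somewhat below the average of 12 months assumed in section 10.1.2.

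For follow-up *T*, P(ever raised) = 1 − exp(−*aT*) and P(ever treated) = 1 − exp(−*bT*). The four cells of the table are the products of these probabilities averaged over *T*, and OR = p11·p00/(p10·p01).

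Example with *a* = 1, *b* = 0.10 and 20% exit: p11 = 0.0578, p10 = 0.5404, p01 = 0.0329, p00 = 0.3689. OR = (0.0578 × 0.3689)/(0.5404 × 0.0329) ≈ 1.20.

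| Early exit | Ever/never OR, no true association |
|---|---|
| 20% | 1.13-1.44 |
| 10% | 1.07-1.24 |
| none (visit window only) | 1.005-1.009 |

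So the artefact is real for that analysis, and almost all of it comes from early exit. At 3750 subjects the 95% confidence factor of this odds ratio is 1.26-1.55. In seven of the eight rate combinations the shift is smaller than that factor; the exception is *a* = 2, *b* = 0.10 (1.435 against 1.38). Wider rates (*a* 0.2-3, *b* 0.03-0.30) with 20% exit give about 1.1 to 2.1, so the quoted range reflects the chosen inputs.

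**2. Does the protocol's wording lead to that analysis?**

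Take the subject-day as the unit. If the daily probability of therapy is *h* whatever the sensor state, the odds are *h*/(1 − *h*) on raised and on other days, and the odds ratio is 1.00 whatever the follow-up. A subject who leaves early contributes fewer days to both groups. In a daily simulation without true association (14 scenarios, some with a raised state following 20% of therapies on the same or next day), relating therapy to the previous day's state gave rate ratios of 0.96-1.04 to first therapy. The daily person-period odds ratio agreed with the rate ratio to within 0.003. That analysis is also an odds ratio in subjects with usable sensor and episode data. The text of sections 10.3 and 10.5.2 therefore covers a sound analysis as well as a poor one.

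**3. Would even the poor analysis be unreadable?**

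With a true rate ratio of 3 and no early exit, the ever/never odds ratio is 1.15-1.51, which overlaps the 1.13-1.44 above. But that sets a study without early exits against one with 20%. With 20% exit on both sides and *b* = 0.10, simulation gave:

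| No association | True rate ratio 3 |
|---|---|
| 1.11 | 1.30 |
| 1.13 | 1.46 |
| 1.18 | 1.40 |
| 1.21 | 1.62 |
| 1.43 | 1.75 |
| 1.46 | 2.12 |

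The rows are *a* = 0.5, 1 and 2 with raised states of 20 or 45 days. The true association gives the higher value in every matched pair. The ever/never table inflates the null and dilutes the signal, but the two do not coincide.

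**The case for a change.** The strongest case for the concern is that section 10.3 presents its entries as the planned methods, fixes measure and set, and does not send this objective to the statistical analysis plan, as sections 10.10 to 10.12 do for other analyses. The set is worded in subjects, and the primary analysis carries a time anchor (admission minus discharge) while this entry has none. Nor is a day-level analysis safe by itself: with the 20% feedback described above, a same-day comparison gives rate ratios of 1.57-5.09 with no true association.

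What stands is the statistics. An untimed ever/never table would be a poor choice, and sensor state should precede the therapy it is related to. What does not stand is the step from silence to error. An analysis set is ordinarily described in subjects even when the records analysed are days or episodes, and the mention of episode data suits such records at least as well. Other entries in section 10.3 are equally brief: cluster analysis without inputs, and a paired t-test for non-HF hospitalizations without a window. Leaving the unit unstated does not select the worst one.

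Nor do the documents support fixing a one-day lag in the protocol and ruling out a 30-day window. Those results follow from a simulation in which risk depends on the current raised state and feedback falls only on the same or next day. If risk outlasts the raised state, or arrhythmia disturbs the sensors for several days before therapy, the ranking of windows is not shown.

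**Conclusion.** The concern does not hold. The synopsis and sections 10.3 and 10.5.2 agree with each other, and what they fix, an odds ratio in subjects with usable sensor and episode data, is compatible with a valid time-linked analysis. The unit, cut-off, window and lag are details commonly left to the statistical analysis plan, and this is an exploratory objective with no formal test or claim attached. The 1.13-1.44 is correct arithmetic for an ever/never per-subject table under 20% early exit and the assumed rates. It falls to 1.07-1.24 with 10% exit and to about 1.01 with none, and it does not arise in a subject-day analysis that takes the sensor state from before the day at risk. It measures a hypothetical choice, not one that the protocol makes. This conclusion rests on the protocol alone. It would change only if the analysis plan adopted the untimed per-subject table.

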### 5.1 Primary Objective

The primary objective of the PREEMPT-HF study is to investigate the association between HF Sensor data and 30-day HF readmissions.

Subjects will be followed for approximately 12 months to collect the required number of clinical events to support the study objectives. These events are called Reviewable Clinical Events (RCEs), and include all-cause hospitalizations and HF outpatient visits (as defined below).

[figure not shown]
RCEs require the investigational site to review the subject's medical records and complete the appropriate eCRF (Figure 3).

Clinical events for the purposes of data analysis are defined as follows:

- **Hospitalization (all-cause):** the subject is admitted to inpatient hospital care and discharged on a different calendar date.
- **HF Hospitalization:** the subject is admitted with signs/symptoms of congestive heart failure (CHF) and receives unscheduled augmented HF therapy with oral or intravenous medications, ultrafiltration therapy or other parenteral therapy.
- **HF Readmission (30-day):** the subject is admitted for an unplanned hospitalization for any cause within 30 days post discharge from a HF hospitalization.
- **HF Outpatient Visit:** the subject has signs/symptoms of congestive HF, and receives unscheduled intravenous decongestive therapy (e.g., IV diuretics, IV inotropes, IV vasoactive drugs, ultrafiltration), in a setting that does not involve a hospitalization (e.g.: emergency room, HF clinic, primary care clinic, etc.).

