**Table 17-1: Safety Definitions**

Term	Definition
	events related to the study medical device.
Adverse Device Effect (ADE)  Ref: ISO 14155  Ref: MEDDEV 2.7/3	Adverse event related to the use of the study medical device NOTE 1: This includes any adverse event resulting from insufficiencies or inadequacies in the instructions for use, the deployment, the implantation, the installation, the operation, or any malfunction of the study medical device. NOTE 2: This definition includes any event resulting from use error or intentional abnormal use of the study medical device.
Serious Adverse Event (SAE)  Ref: ISO 14155  Ref: MEDDEV 2.7/3	Note: This definition meets the reporting objectives and requirements of ISO 14155 and MEDDEV 2.7/3. Adverse event that: a) Led to death, b) Led to serious deterioration in the health of the subject as defined by either: 
 
• a life-threatening illness or injury, or
 
• a permanent impairment of a body structure or a body function, or
 
• in-patient hospitalization or prolongation of existing hospitalization, or
 
• medical or surgical intervention to prevent life-threatening illness or injury or permanent impairment to a body structure or a body function
 
 c) Led to fetal distress, fetal death, or a congenital abnormality or birth defect. NOTE 1: Planned hospitalization for a pre-existing condition, or a procedure required by the clinical investigational plan, without a serious deterioration in health, is not considered a serious adverse event.
Serious Adverse Device Effect (SADE)  Ref: ISO 14155  Ref: MEDDEV 2.7/3	Adverse device effect that has resulted in any of the consequences characteristic of a serious adverse event.
Unanticipated Adverse Device Effect (UADE)  Ref: 21 CFR Part 812	Any serious adverse effect on health or safety or any life-threatening problem or death caused by, or associated with, a device, if that effect, problem, or death was not previously identified in nature, severity, or degree of incidence in the investigational plan or application (including a supplementary plan or application), or any other unanticipated serious problem associated with a device that relates to the rights, safety, or welfare of subjects.

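### The non-HF hospitalization analysis mixes planned and unplanned stays, which can bias the mean sensor change (exploratory objective, low priority)

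*Protocol*

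**What the plan says.** The analysis set for this objective appears twice. Section 10.3 states: "All subjects with a non-HF hospitalizations and usable sensor data will be included in the analysis". Section 10.5.2 restates it: "All subjects with a non-HF hospitalization and usable sensor data will be included in the analysis of characterizing HF sensors for association with non-HF hospitalizations". On the method, Section 10.3 says: "This will be assessed using a paired t-test". The synopsis adds that there is one such test per HF sensor. Neither section limits the set to unplanned stays.

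Section 5.1 counts a stay as a hospitalization when "the subject is admitted to inpatient hospital care and discharged on a different calendar date". An elective stay with an overnight date change qualifies.

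For other events the protocol does separate acute from scheduled care:

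- A 30-day HF readmission means that "the subject is admitted for an unplanned hospitalization for any cause within 30 days post discharge from a HF hospitalization" (Section 5.1).
- An HF hospitalization requires that the subject "receives unscheduled augmented HF therapy with oral or intravenous medications, ultrafiltration therapy or other parenteral therapy" (Section 5.1). The HF outpatient visit likewise requires unscheduled therapy.
- Note 1 to the SAE definition in Table 17-1 sets apart: "Planned hospitalization for a pre-existing condition, or a procedure required by the clinical investigational plan, without a serious deterioration in health".

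Appendix 25.2 lists Cardiac Procedure and Orthopedic among the primary organ causes. Sections 8.2 and 17.1 remove one kind of procedural admission, device or lead revision or explant, by withdrawing the subject.

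**The concern.** Section 3.1(4) motivates this objective by noting that about three of four hospitalizations in HF patients are unrelated to HF, and that strategies to reduce hospitalizations should cover cardiac and non-cardiac conditions. For that purpose the useful quantity is the sensor change that accompanies illness leading to admission.

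A stay booked in advance, such as some of those under Cardiac Procedure or Orthopedic, need not follow any deterioration. If the paired comparison looks at the period before admission, such stays pull the mean change toward zero. If the window extends into or past the stay, the procedure and the immobility that follows can move the sensors by themselves. A pooled mean can therefore be too small, or partly procedure-driven, and the reader cannot tell which. In an exploratory study the estimate is the main product, so its interpretability matters even without a formal hypothesis.

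**Working it through.** **Figures in the plan.** No sample size or power is stated for the non-HF test. The only sizing is for the primary objective (Section 10.1.2), and it reproduces. For a standardized difference of 0.5, two-sided alpha 0.05 and a 3:1 ratio, 43 against 129 gives 80.6% power by the noncentral t. Then 43 / 0.20 = 215; 215 / 0.80 = 268.75, stated as 270; and 270 / (0.09 × 0.80) = 3750. None of this uses non-HF stays, so the present point leaves it unchanged.

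**Bias in the mean.** Let f be the planned share, μ the mean change in unplanned stays and g the mean change in planned stays. The pooled mean is

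(1 − f)μ + f·g.

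The document gives none of these, so the values below are assumptions.

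- No change in planned stays (g = 0): the pooled mean is (1 − f)μ, a shrinkage of 10%, 20%, 30% or 40% for f = 10%, 20%, 30% or 40%.
- No change in unplanned stays (μ = 0) and a procedure-related shift of g = 0.3 SD: the pooled mean is 0.3f, from 0.03 SD at f = 10% to 0.12 SD at f = 40%. All of it comes from planned stays.

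**Effect on the test.** With g = 0 and an unplanned change of d SD, the pooled standardized change is (1 − f)d / √(1 + f(1 − f)d²). For d = 0.3, 90 stays give 80% power if all are unplanned (two-sided alpha 0.05, noncentral t):

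| f | Pooled change (SD) | Stays for 80% power | Power, all 90 stays | Power, unplanned only |
|---|---|---|---|---|
| 10% | 0.27 | 111 | 71% | 76% (81 stays) |
| 20% | 0.24 | 141 | 61% | 71% (72 stays) |
| 30% | 0.21 | 184 | 50% | 65% (63 stays) |
| 40% | 0.18 | 250 | 39% | 58% (54 stays) |

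Under these assumptions, dropping planned stays gains power despite the smaller number.

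**At a plausible study size.** Taking three non-HF stays per HF stay (Section 3.1(4)) and the 270 index HF hospitalizations gives 3 × 270 = 810 stays. This is a rough guide only: the 270 are first HF events, and stays are treated as independent. With g = 0:

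- d = 0.2 SD: power is above 99% at f = 20% and 92% at f = 40%.
- d = 0.1 SD: power falls from 81% (f = 0) to 62% (f = 20%) or 40% (f = 40%).

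In the reverse case (μ = 0, g = 0.3 SD), the test at 810 stays rejects 14%, 40%, 72% or 92% of the time for f = 10%, 20%, 30% or 40%. It would be detecting a real pooled change, but one that comes only from planned stays.

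**The case against.** The strongest reply has four parts.

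1. **The windows are not stated.** Dilution needs a window before admission; procedure effects mainly need one reaching into or past the stay. Windows are commonly left to the SAP, so their absence is no finding, and neither mechanism can be asserted outright. This stands. The analysis set, however, is fixed in the protocol itself, twice and without a limit.

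2. **Part of the mixture is already separated.** The objective names cardiac non-HF and non-cardiac events. Section 9.8 requires classification by primary organ cause for subgroup analysis, Section 19.2 has the sponsor extract context for each event, stays without a date change do not count, and device or lead revisions leave the study. This stands as mitigation. Organ cause does not distinguish planned from acute stays within classes such as Arrhythmia, Vascular or Orthopedic.

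3. **Describing all non-HF stays is a legitimate aim, and the unplanned limit on readmissions serves a different objective.** A reader might infer that the protocol contradicts itself. It does not; it draws a distinction elsewhere and leaves it out here. But a pooled description serves the purpose in Section 3.1(4) poorly.

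4. **The size has no source in the document.** The wording of Note 1 in Table 17-1 leaves room for planned stays that do involve deterioration, so zero change in all planned stays is itself doubtful. A reader might infer from the table above that the test needs about 1.6 to 2.8 times as many events (141/90 and 250/90). The document does not support that as a consequence for this study: it sets no power for the test, and at about 810 stays power stays above 90% for changes of 0.2 SD or more even at f = 40%.

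**Conclusion.** The point holds as a matter of interpretation. Sections 10.3 and 10.5.2 put planned and unplanned non-HF stays into one paired t-test per sensor, and organ-cause subgroups undo this only in part. The likely harm is a biased mean change, and loss of power is secondary.

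The size cannot be derived from the document. If a share f of stays is planned and has no pre-event change, the mean shrinks by f: 10-40% over the assumed range. If the window catches the procedure, the bias may instead add change unrelated to the illness.

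This concerns one exploratory additional objective, for which Section 10.6 plans no formal tests or claims. The primary analysis is untouched. The priority is low.

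**What to change.** - Record planned or unplanned status for every hospitalization on the Reviewable Clinical Event form, unless it is already captured (the form is not shown).
- In Sections 10.3 and 10.5.2, make unplanned non-HF hospitalizations the main analysis set.
- Report planned stays separately, as a comparison set for the pre-event change. Some may involve deterioration, so they are an imperfect negative control.

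The cost is one form item, a short change to two sections, and fewer events in the main test. No data are discarded. The investigator already reviews the records of each hospitalization to classify its cause (Section 9.8), and must already judge planned status for admissions within 30 days of an HF discharge. The item is best added while enrollment continues, since recovering the status later means going back to the records.
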